Enhancing Locomotor Learning with Motor Imagery and Transcranial Direct Current Stimulation: A Pilot Randomized Controlled Trial in Young Adults.

NCT06414213

09-20-2022

Study protocol

Study Design

The primary goal of this study is to investigate an novel intervention on improvements in walking and balance. The design of this study is a randomized, double-blinded clinical trial. The study will use a pilot intervention that will utilize a dual strategy combining MI with tDCS (a non-invasive brain stimulation) to activate the frontal/executive networks of the brain to enhance motor learning to increase retention and transfer of locomotor learning. Participants, separated by age by age 18-35 and 50 and older, will be randomly allocated to experimental (active tDCS) or sham groups and will be assessed at baseline, immediately following the intervention, and at 1-week. Outcome measures include cortical activation (oxygenated Hemoglobin, HbO₂), assessed through functional near-infrared spectroscopy (fNIRS), cognitive assessments, and gait and balance assessments. Complete participation will consist of 2 visits to the Neuromechanics laboratory at Leon Levine Hall.

Outcome Measures

Assessments will be conducted by the experienced examiner(s) blinded to group tDCS assignment and will occur at three time points: baseline, post-Intervention, and follow-up (1 week after the baseline assessment). Prefrontal cortical activity will be assessed during walking to investigate intervention-induced prefrontal/executive activity changes. Using a commercially available Functional near infrared spectroscopy (fNIRS) monitor (OctaMon by Artinis Medical Systems), changes in oxygenated hemoglobin concentration (O₂Hb) relative to a baseline task will be measured for the orbitofrontal and dorsolateral prefrontal cortex. During walking assessments, we will use fNIRS to measure frontal cortical activity. Changes in O₂Hb will be assessed at baseline and after the intervention week. All manufacturer guidelines will be followed in the collection of fNIRS.

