Time to completion: Participants will walk over a 4-m instrumented walkway mat during the assessments. The walkway system is a clinical instrument that allows for objective gait assessment. Spatial and temporal gait variables calculated from the walkway system have strong concurrent validity and test-retest reliability (intra-class coefficients >0.8 for most variables). These measures will allow us to determine time to completion and changes in gait quality (stepping characteristics) during pre/post/ and follow-up testing.

Kinesthetic and Visual Imagery Questionnaire (KVIQ): The ability to imagine movements was assessed with the KVIQ. This test evaluates the subject's ability to see (visual imagery) and feel (kinesthetic imagery) movements. The KVIQ consists of 10 items, (5 movements for each scale), each item being a separate movement followed by rating the ease or difficulty of generating those self-images on a 5-point Likert scale (where 1 = no image or sensation and 5 = Image as clear as seeing or as intense as executing the action). Higher scores reflected higher imagery abilities.

Baseline visit and Intervention

We will enroll 40 adults age 18 to 35 (n=20) and 50 and older (n=20) without neurological conditions. Participants will be randomized to one of the two groups: 1) MI with sham tDCS ('MI /sham') and 2) MI with active tDCS ('MI/ active').

For Visit One, All participants will undergo fNIRS, Gait assessment, and KVIQ. Additionally, all participants will perform the locomotor learning task.

Locomotor Learning

Participants will begin in a quiet, standing position with the fNIRS attached to themselves and after a period of 30 secs of quiet rest, participants will stand for a period of 30 secs and then begin walking over the course. The course is a 10-meter obstacle course containing foam obstacles of various heights and widths at their fastest safe pace. Participants will repeat this process 10 times. Participants will be asked not to speak and only engage in thinking about the walking course. Rest periods of a minimum of 1 min will be permitted to prevent fatigue and standardize the procedures. Time to complete the course will be recorded and the change in time to complete the course will be used as an outcome.

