is an appropriate duration for observational learning protocols to observe improvements. The model video sequence will show a typical pass through the complex walking course by a gender matched model.

Follow up

All participants will then return after one week and repeat the baseline assessments. Including the fNIRS, Gait assessment, and KVIQ and the locomotor learning task.

Statistical Design

Times of the three trials at each test will be averaged to observe any learning effects during the obstacle course. $\Delta\text{O}_2\text{Hb}$ at each of the 3 trials during each test were averaged. A 2-way factorial ANOVA with a between-subjects factor of group (3 levels) and a within-subjects factor of time (3 levels) will be used. In the case of significant interactions of main effects, pairwise comparisons using Fisher's LSD will be used post-hoc. Effect sizes will be interpreted from partial eta squared as small=0.01, medium=0.06, and large=0.14. Independent samples t-tests will be used to analyze any differences in the MIQ-3, and the tDCS sensitivity between groups.

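### The effect-size labels rest on uncorrected partial eta squared with no interval, so at this sample size most null interactions would be described as at least 'small'

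*Combined protocol and SAP*

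**What the plan says.** The combined protocol and SAP has one rule on effect size, in Statistical Design: "Effect sizes will be interpreted from partial eta squared as small=0.01, medium=0.06, and large=0.14". That section mentions no bias correction and no confidence interval.

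The analysis that produces the measure is given just before it: "A 2-way factorial ANOVA with a between-subjects factor of group (3 levels) and a within-subjects factor of time (3 levels) will be used". Significance is then used as a gate, but only for the follow-up comparisons: "In the case of significant interactions of main effects, pairwise comparisons using Fisher's LSD will be used post-hoc". No such condition is placed on the effect-size labels.

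Three other statements fix the sample size and the degrees of freedom:
- Baseline visit and Intervention: "We will enroll 40 adults age 18 to 35 (n=20) and 50 and older (n=20) without neurological conditions".
- The same section: "Participants will be randomized to one of the two groups", namely motor imagery with sham and motor imagery with active tDCS. This disagrees with the three-level group factor in Statistical Design.
- Study Design: participants "will be assessed at baseline, immediately following the intervention, and at 1-week", which gives three times.

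The title describes the study as "A Pilot Randomized Controlled Trial in Young Adults", so an analysis of the 20 younger participants alone is a plausible reading. The documents give no alpha, power, target effect, standard deviation or dropout rate.

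**The concern.** Partial eta squared cannot be negative, so chance variation alone pushes it above zero. In a sample of this size, its average under no effect exceeds the 0.01 cut-off for a small effect. A verbal scale applied to the raw value will therefore often attach a size word to noise.

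A second problem is that the partial measure for a within-subject interaction removes stable between-person variation from its denominator. The same benefit in seconds can then earn a different word depending only on how strongly repeated measurements correlate.

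At stake is what the trial can say about the size of the effect. A label without an interval does not show how little 40 people, or 20, can tell us about that size. Nor does it give the reader the difference in seconds or in O2Hb.

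**Working it through.** The plan has no sample-size or effect-size figure to reproduce, so the check is of how the stated rule behaves when there is no true effect.

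**Inputs from the documents.** N = 40, or 20 for the young adults; g = 2 randomised groups, or 3 as the ANOVA is written; 3 times; cut-offs 0.01, 0.06 and 0.14.

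**Assumptions.** Normal errors, sphericity, no dropout.

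**Formula.** Partial eta squared is SS_effect / (SS_effect + SS_error). Under no effect it follows Beta(df1/2, df2/2), with mean df1/(df1 + df2). For the group-by-time interaction, df1 = 2(g − 1) and df2 = 2(N − g).

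**N = 40, g = 2.** The df are (2, 76), so the distribution is Beta(1, 38) and P(≥ c) = (1 − c)^38.
- Mean: 2/78 = 0.026.
- At least small: 0.99^38 = 68.3%.
- At least medium: 0.94^38 = 9.5%.
- Large: 0.86^38 = 0.3%.

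**N = 40, g = 3.** The df are (4, 74), so the distribution is Beta(2, 37) and P(≥ c) = (1 − c)^37 × (1 + 37c).
- Mean: 4/78 = 0.051.
- At least small: 0.99^37 × 1.37 = 94.5%.
- At least medium: 0.94^37 × 3.22 = 32.6%.
- Large: 0.86^37 × 6.18 = 2.3%.

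**N = 20, g = 2.** The df are (2, 36), so the distribution is Beta(1, 18) and P(≥ c) = (1 − c)^18.
- Mean: 2/38 = 0.053.
- At least small: 0.99^18 = 83.5%.
- At least medium: 0.94^18 = 32.8%.
- Large: 0.86^18 = 6.6%.

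**Robustness.** Simulation with 40,000 replicates and two groups gave 68.6% at least small at N = 40 and 83.5% at N = 20 under compound symmetry. Under one non-spherical covariance it gave 63% and 80%. For the group main effect at N = 40 with two groups, df (1, 38), the figures are 53.9%, 12.8% and 1.7%. If dropout left 32 participants in two groups, the interaction figure for at least small would be 74%.

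**Dependence on correlation.** Assume an arm difference of 0.3 SD at both post-baseline times, none at baseline, and compound symmetry with correlation rho. The arm differences are 0, 0.3 and 0.3, with mean 0.2. Halving the deviations from that mean gives interaction effects of −0.1, 0.05 and 0.05, whose squares sum to 0.015. The error term per participant is 2(1 − rho). The population value is 0.015 / (0.015 + 2(1 − rho)):

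| rho (assumed) | partial eta squared | label |
|---|---|---|
| 0.3 | 0.015/1.415 = 0.011 | small |
| 0.5 | 0.015/1.015 = 0.015 | small |
| 0.7 | 0.015/0.615 = 0.024 | small |
| 0.9 | 0.015/0.215 = 0.070 | medium |

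**Would bias correction alone be enough?** Partial epsilon squared, (SS_effect − df1 × MS_error)/(SS_effect + SS_error), averages about zero under no effect. It reaches 0.01 when partial eta squared reaches (0.01 + df1/df2)/(1 + df1/df2). With two groups this is 0.0354 at N = 40, so the probability is (1 − 0.0354)^38 = 25%. At N = 20 it is 0.0621, and (1 − 0.0621)^18 = 32%. The bias goes, but a quarter to a third of null interactions still earn a label.

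**The case against.** The strongest reply is that the labels decide nothing. The F tests carry the inference and their Type I error is untouched. At an assumed alpha of 0.05, the two-group interaction at N = 40 is significant only when partial eta squared is at least 1 − 0.05^(1/38) = 0.076, so a null result in the small band would be reported as non-significant. Most false labels in that design are the mildest word: fewer than one in ten reach medium. The cut-offs are a verbal scale, and dependence on within-subject correlation is a known property of the measure. Pairwise comparisons of mean times would also bring out differences in seconds.

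Much of this stands, and it rules out two stronger readings. A reader might infer that the plan will usually declare an effect when there is none. The documents do not support that: they test by ANOVA and nowhere treat a label as evidence that an effect exists. A reader might also infer that the labels will drive a go/no-go decision or size a later trial. The study is called a pilot, but no such rule or use is stated.

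What does not stand is the idea that significance contains the problem. The plan does not confine labels to significant effects. At N = 20 with two groups the significance threshold is 1 − 0.05^(1/18) = 0.153, so even a large label can accompany a non-significant result. The pairwise comparisons are promised only after significance, and no interval is promised at all.

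**Conclusion.** The concern holds as a point about description, not about testing. On every reading of the design examined, more than half of null effects would carry at least the small label. With 40 participants and two groups, false labels are almost all small. The problem is materially worse with a three-level group factor or an analysis of 20, where about a third of null interactions would be called medium or larger.

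The exact figures rest on normal errors, sphericity and complete data; the non-spherical case tried lowered the interaction figures modestly. The range of 0.011 to 0.070 for one fixed benefit rests on an assumed 0.3-SD difference and assumed correlations, none of which the documents give. The change is worth making because it alters what the trial can conclude about effect size, but no test or stated decision depends on it.

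**What to change.** Replace the labelling sentence in Statistical Design with a commitment to report the active-minus-sham difference in course time (seconds) and in O2Hb, each with a 95% CI, at every post-baseline time at which the outcome is measured. State that these are reported whether or not the F test is significant. Drop the words small, medium and large.

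If a variance-explained measure is kept, use a bias-corrected one (omega or epsilon squared) with a CI. Changing the estimator while keeping the labels is not enough.

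Separately, reconcile the number of group levels in the ANOVA with the two randomised groups, and state whether the analysis set is all 40 participants or the young adults alone, since both change the size of the bias.

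The cost is a wording change and one extra output line from data already being collected. Reported effects will look smaller and less certain.
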